2.4.2 Concomitant medications

Concomitant medications will be coded using GSK Drug coding dictionary, summarized, and listed. The summary of concomitant medications will show the number and percentage of subjects taking concomitant medications by Ingredient. Multi-ingredient products will be

summarized by their separate ingredients rather than as a combination of ingredients. Anatomical Therapeutic Chemical (ATC) classification Level 1 (Body System) information will be included in the dataset created but will not appear on the listing or summary.

In the summary of concomitant medications, each subject is counted once within each unique ingredient. For example, if a subject takes Amoxicillin on two separate occasions, the subject is counted only once under the ingredient “Amoxicillin”.

2.5 Analysis of the primary objective

The primary objective of the study is to determine the efficacy of prophylactic octreotide in reducing the proportion of subjects experiencing diarrhoea with a severity of National Cancer Institute Common Terminology Criteria for Adverse Events (NCI-CTCAE) Grade 2 and above during the first 3 cycles of treatment with lapatinib and capecitabine.

2.5.1 Primary endpoint

The primary efficacy endpoint is proportion of subjects experiencing diarrhoea with a severity of Grade 2 and above during the first 3 cycles of treatment with lapatinib and capecitabine, as defined by the NCI-CTCAE, version 4.03 (see Appendix 1 Table 1 of the study protocol).

2.5.2 Statistical hypothesis, model, and method of analysis

2.5.2.1 Diarrhoea of Grade 2 and above during the first 3 cycles treatment

This study is designed to test the superiority of prophylactic octreotide vs. no prophylactic octreotide in reducing the proportion of subjects experiencing diarrhoea with a severity of 2 or higher during the first 9 weeks (i.e., 3 cycles treatment) of lapatinib and capecitabine. Superiority will be assessed using data from the Intent-to-Treat population. The following statistical hypothesis will be tested to address the primary efficacy objective:

$$H_0: \delta = 0 \text{ vs. } H_a: \delta < 0,$$

where δ is the difference in the incidence of Grade 2 or higher diarrhoea between prophylactic vs. no prophylactic octreotide during the first 3 cycles of lapatinib and capecitabine.

The AE term ‘diarrhoea’ will be used to select episodes of diarrhoea.

Episodes of diarrhoea ‘during the first 3 cycles of treatment’ are defined as those with an onset date on or after the efficacy reference start date as defined in [Section 2.1.3.2](#) and before the Cycle 4 visit date.

Subjects who withdraw from the study on or prior to the Cycle 4 visit date will be assumed to have experienced diarrhoea (non-responder imputation) of grade 2 or higher.

The superiority of prophylactic octreotide compared to no prophylactic octreotide will be assessed using a Pearson chi-square test in ITT population. The implementation of the Pearson chi-square test is specified in [Section 5.3.1](#). The proportion of subjects experiencing at least one episode of diarrhoea with a severity of Grade 2 or higher in each treatment group, the difference in proportions between the treatment groups, the corresponding 95% confidence interval and the two-sided p-value from the chi-square test will be presented.

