#### **4.3.2. Discontinuation from Treatment with Lapatinib and Capecitabine**

Subjects may withdraw from the study at any time.

Study treatment may be permanently discontinued for any of the following reasons:

- liver chemistry meeting the stopping criteria described in Section 5.13.1
- deviation(s) from the protocol
- disease progression
- request of the subject or proxy
- investigator's discretion
- subject is lost to follow-up
- study is closed or terminated.

The primary reason study treatment was permanently discontinued must be documented in the subject's medical records and the study eCRF. If the subject voluntarily discontinues treatment due to toxicity, 'AE' will be recorded as the primary reason for permanent discontinuation in the eCRF.

Subjects who require permanent discontinuation of either lapatinib or capecitabine must permanently discontinue both treatments in that combination and the reason for discontinuation must be recorded. Once a subject has permanently discontinued treatment with lapatinib and capecitabine, the subject will not be allowed to be re-treated and must be withdrawn from the study.

All subjects who discontinue treatment with lapatinib and capecitabine will have safety assessments at the time of discontinuation as specified in the Time and Events Schedule (Table 16 and Table 17) and in Section 7.1.8.

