### **9.3.5. Key Elements of Analysis Plan**

The final analysis will take place when all subjects have completed the study.

Data will be listed and summarised according to the GSK reporting standards, where applicable. Complete details will be documented in the Reporting and Analysis Plan (RAP). Any deviations from, or additions to, the original analysis plan described in this protocol will be documented in the RAP and final study report.

As it is anticipated that accrual will be spread thinly across centers and summaries of data by center would be unlikely to be informative, data from all participating centers will be pooled prior to analysis.

All data up to the time of study completion (24 weeks or early withdrawal from the study) will be included in the summaries, regardless of the duration of treatment.

As the duration of treatment for a given subject will depend on efficacy and tolerability, the duration of treatment will vary between subjects. Non-responder imputation will be used in the case of missing data for the analysis of the primary endpoint based on the ITT population. Subjects who withdraw from the study prior to the Week 9 visit without experiencing Grade 2 diarrhoea or above will be assumed to have experienced Grade 2 diarrhoea or above for the purpose of the analysis. Similar imputation techniques will be

used for the m-ITT population analysis of the primary endpoint. No imputation will be performed for the Per Protocol analyses. Imputation methods for the secondary endpoints will be considered and detailed as appropriate in the RAP.

Demographic and screening characteristics will be summarised.

Details on the determination of tumour response are given in Section 7.1.11. There will be no adjustments for multiplicity.

Details on efficacy summaries are provided in Section 9.3.5.1 and details on safety summaries are provided in Section 9.3.5.2.

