2.2 Analysis Populations

Intent-to-Treat Population

The Intent-to-Treat (ITT) population will comprise all randomised subjects regardless of whether or not treatment was administered. This population will be based on the treatment to which the subject was randomised. Any subject who receives a treatment randomization number will be considered to have been randomised. The primary analysis of disease efficacy and all diarrhoea-related efficacy endpoints will be analysed using the ITT population.

Modified ITT

The modified ITT (m-ITT) population will comprise all subjects in the ITT population and under Octreotide arm this population will include subjects who do not show intolerance to octreotide in the s.c. formulation and who do not have non treatment related diarrhoea recorded

as an AE after the first dose of octreotide LAR and prior to the start of treatment with lapatinib and capecitabine. A sensitivity analysis of diarrhoea-related primary efficacy endpoint will be conducted using the m-ITT population.

Per Protocol Population

The Per-Protocol (PP) population will comprise all randomised subjects who receive at least one dose of study treatment and who comply closely with the protocol (that is subjects who are not excluded from PP set as per PDMP). The PP population will not be analysed if this population comprises more than 95% or less than 50% of the ITT population. The analysis of primary efficacy endpoint will be repeated using the PP population.

Subjects with potential PDs will be excluded from PP population based on Protocol Deviation Management Plan (PDMP).

Safety Population

The Safety population will comprise all randomised subjects who receive at least one dose of study treatment and will be based on the actual treatment received if this differs from that to which the subject was randomised. This population will be used for the analysis of clinical safety data. Moreover, if a subject who was randomised to Octreotide arm, showed intolerance to octreotide in the s.c. formulation, and took at least one dose of lapatinib or capecitabine, then subject will be included in no Octreotide arm for safety analysis.

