2.5.3 Handling of missing values/censoring/discontinuations

Diarrhoea with a severity of 2 or higher during the first 9 weeks (i.e., 3 cycles treatment): Subjects who withdraw from the study on or prior to the Cycle 4 visit date will be assumed to have experienced diarrhoea (non-responder imputation) of grade 2 or higher. Such an imputation techniques will be used for the ITT and m-ITT population analysis of the primary endpoint. No imputation will be performed for the Per Protocol analyses.

Diarrhoea with a severity of 2 or higher during the entire treatment period: Subjects who do not have diarrhea event prior to the End of Study/Withdrawal visit date will be considered as non-responders and no imputation will be done in such cases.

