2.5.4 Supportive analyse

Supportive analyses of the primary endpoint will be conducted using the m-ITT and PP populations, using the same methods as defined for the primary analysis. The primary endpoint will be summarized using the m-ITT and PP populations, but there will not be any statistical test performed for these populations.

No imputation will be used for the PP analysis, i.e., patients without any diarrhea event on or before desired timepoint will not be imputed and considered as non-responders.

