3.2 Sample Size Sensitivity

Based on the results of EGF111438, an incidence of 20% of Grade 2 or higher diarrhoea is assumed for subjects who receive lapatinib and capecitabine with no prophylactic octreotide. The power for the analysis to detect a reduction in the incidence of Grade 2 or higher diarrhoea from 14% to 8% ranges from 69% to 25%, if the assumed incidence in the control group is 20%, using a one-sided test with an alpha level of 0.025 ([Table 3-1](#)).

Table 3-1 Sensitivity of sample size based on 20% control incidence of Grade 2 or more diarrhoea

Incidence, no prophylactic octreotide	20%	20%	20%	20%	20%
Incidence, prophylactic octreotide	6%	7%	8%	10%	12%
Estimated Statistical Power	69%	61%	53%	37%	25%
Subjects per Treatment group	70	70	70	70	70

Based on the results of EGF100151, an incidence of 32% of Grade 2 or higher diarrhoea is assumed for subjects who receive lapatinib and capecitabine with no prophylactic octreotide. The power for the analysis to detect a reduction in the incidence of Grade 2 or higher diarrhoea from 20% to 12% ranges from 82% to 36%, if the assumed incidence in the control group is 32%, using a one-sided test with an alpha level of 0.025 ([Table 3-2](#)) [Table 3-2](#).

Table 3-2 Sensitivity of sample size based on 32% control incidence of Grade 2 or more diarrhoea

Incidence, no prophylactic octreotide	32%	32%	32%	32%	32%
Incidence, prophylactic octreotide	12%	14%	16%	18%	20%
Estimated Statistical Power	82%	72%	60%	48%	36%
Subjects per Treatment group	70	70	70	70	70

Power calculations were performed using nQuery software version 7.0.

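### The 9-week ITT result counts any study withdrawal up to the Cycle 4 visit as Grade 2+ diarrhoea, and no planned ITT analysis shows the recorded 9-week incidence beside it

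*SAP*

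**What the plan says.** - **Objective.** SAP 2.5 sets out "to determine the efficacy of prophylactic octreotide in reducing the proportion of subjects experiencing diarrhoea" of Grade 2 and above during the first three cycles of lapatinib and capecitabine.
- **ITT and m-ITT at 9 weeks.** Under SAP 2.5.2.1, a subject who leaves the study on or before the Cycle 4 visit "will be assumed to have experienced diarrhoea (non-responder imputation) of grade 2 or higher". SAP 2.5.3 applies this to both populations. Neither section separates reasons for leaving.
- **Protocol.** Section 9.3.5 has the same rule: a subject who leaves before the Week 9 visit without such an event "will be assumed to have experienced Grade 2 diarrhoea or above for the purpose of the analysis".
- **Per protocol (PP) at 9 weeks.** SAP 2.5.3 says "No imputation will be performed for the Per Protocol analyses". SAP 2.5.4 adds that "patients without any diarrhea event on or before desired timepoint will not be imputed and considered as non-responders", and that there is no test. SAP 5.3.1 defines a response as having the event, so a non-responder here is a subject without diarrhoea. In SAP 2.5.2.1 the same label means a subject with it.
- **PP availability.** SAP 2.2: "The PP population will not be analysed if this population comprises more than 95% or less than 50% of the ITT population".
- **Nearby analyses.** SAP 2.5.2.2 and 2.5.3 plan an ITT summary of Grade 2+ diarrhoea without imputation, but over the whole treatment period. SAP 2.6.1.3 plans a Kaplan-Meier analysis that censors withdrawals, but for diarrhoea of any grade.

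**The concern.** The quantity in the objective is the 9-week incidence of Grade 2+ diarrhoea. The quantity reported under that name is Grade 2+ diarrhoea or leaving the study. A subject who withdraws consent, stops for an unrelated toxicity, or leaves before taking any lapatinib or capecitabine adds to the diarrhoea rate.

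The PP summary goes to the other extreme in a different population. A reader of the final report therefore has no ITT figure for recorded events at 9 weeks. A null result could not be separated into no effect of octreotide and withdrawals for other reasons.

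The arms are also exposed unequally. Under SAP 2.1.3.2 the efficacy clock starts at randomisation. Under SAP 1.1 the octreotide arm starts lapatinib and capecitabine 7 days after the first LAR dose, while the control arm starts at once. Octreotide subjects thus have about one further week in which leaving becomes an event.

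**Working it through.** **Inputs.** Rates of 20% (control) and 6% (octreotide) and 70 per arm come from SAP 3.1 and 3.2. The withdrawal proportion w by week 9 is not in either document. I assume 5% to 20%, independent of diarrhoea.

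**Reproducing the plan's power.** The stated power is for a comparison "using a one-sided test with an alpha level of 0.025". The pooled normal approximation without continuity correction is Φ[(d√n − 1.96√(2p̄q̄)) / √(p₁q₁ + p₂q₂)].

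- For 20% v 6%, p̄ = 0.13: (0.14 × 8.367 − 1.96 × 0.4756) / 0.4652 = 0.514, which gives 69.6% (stated 69%).
- All ten entries agree within about one point: 69.6/61.6/53.5/38.0/25.0% against 69/61/53/37/25%, and 82.2/72.0/60.3/48.1/36.5% against 82/72/60/48/36%.

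The tabulated power makes no allowance for withdrawal.

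**Equal withdrawal.** The imputed rate is w + (1 − w)p, so the difference becomes (1 − w)(p_c − p_t).

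| w | Control | Octreotide | Difference (points) | Power, 70 per arm |
|---|---|---|---|---|
| 0 | 20.0% | 6.0% | 14.0 | 69.6% |
| 5% | 24.0% | 10.7% | 13.3 | 54.8% |
| 10% | 28.0% | 15.4% | 12.6 | 43.9% |
| 15% | 32.0% | 20.1% | 11.9 | 36.0% |
| 20% | 36.0% | 24.8% | 11.2 | 30.0% |

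Scoring leavers as event-free also shrinks the difference. At w = 10% it gives at worst 18.0% v 5.4%, or 12.6 points. It is the worst case because a leaver with a recorded event still counts.

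**Unequal withdrawal.**

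| True rates | w control / octreotide | Reported | Difference (points) |
|---|---|---|---|
| 20% v 20% | 15% / 5% | 32.0% v 24.0% | 8.0 (true 0) |
| 20% v 6% | 15% / 5% | 32.0% v 10.7% | 21.3 (true 14) |
| 20% v 6% | 5% / 15% | 24.0% v 20.1% | 3.9 (true 14) |
| 20% v 6% | 5% / 20% | 24.0% v 24.8% | −0.8 (true 14) |

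**Run-in week.** Assume a constant withdrawal rate, so that the octreotide arm has 1 − (1 − w)^(10/9).

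- w = 5% becomes 5.5%. The octreotide rate is 1 − 0.94 × 0.9446 = 11.2%, and the difference is 12.8 rather than 13.3 points.
- w = 20% becomes 22.0%. The octreotide rate is 1 − 0.94 × 0.7804 = 26.6%, and the difference is 9.4 rather than 11.2 points.

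**Scale at the actual size.** SAP section 1 reports 62 patients enrolled. With an assumed 31 per arm, one imputed subject moves an arm's rate by 1/31 = 3.2 points.

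**The case against.** **The rule is the protocol's.** It is openly labelled, and a conservative composite is a legitimate choice for a superiority test. The SAP was also written after the futility result. This stands, and it rules out replacing the primary imputation now. It does not argue against a companion analysis, and SAP 5.1 itself calls for a review of which analyses remain appropriate if the study is terminated.

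**Much is covered elsewhere.** Besides the two nearby analyses, SAP 2.6.1.2 lists every diarrhoea event with its time to onset, and SAP 2.3.1 tabulates withdrawal reasons. That is true, but none gives 9-week Grade 2+ incidence in ITT or separates recorded from imputed events.

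**A reader might infer a far larger loss.** Protocol 1.1 cites a median PFS of 28.6 weeks. If exponential, 1 − 0.5^(9/28.6) = 19.6% have progressed or died by week 9. Protocol 4.3.2 says that after permanent discontinuation "the subject will not be allowed to be re-treated and must be withdrawn from the study". Adding the run-in week then suggests attenuation well above 20%. The documents do not establish this. Protocol 4.3.3 counts progression or death on treatment as completing the study, and on that reading these subjects are not imputed. Disease assessment is also not mandatory between screening and the end-of-study visit, so progression detected in the run-in week is unlikely.

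**A reader might also infer that the effect is always diluted.** That holds only when withdrawal is similar in the arms.

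**The trial is small.** At 31 per arm, 20% v 6% has a 95% half-width of 1.96 × √[(0.16 + 0.0564)/31], about 16 points, so a modest attenuation lies well inside the noise. Planned power is also moot after the stop. Both points stand and limit the weight of this one.

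**Conclusion.** The point holds as a gap in reporting. The 9-week ITT and m-ITT analyses present a composite under the name of diarrhoea, and no planned ITT analysis gives the recorded 9-week Grade 2+ incidence that the objective asks about.

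The distortion has no fixed direction. With equal withdrawal independent of diarrhoea, the difference is multiplied by (1 − w), a 5% to 20% attenuation over the assumed range, and the run-in week takes a little more. With unequal withdrawal, which is possible in an open-label trial with a delayed start in one arm, the effect can be exaggerated, erased or reversed. All sizes rest on assumed withdrawal rates.

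Two matters in the documents decide who is imputed. Protocol 4.3.2 and 4.3.3 disagree on early progression and death. The cut-off also differs: SAP 2.5.2.1 includes the day of the Cycle 4 visit, Protocol 9.3.5 stops before the Week 9 visit, and SAP 5.1 stops before the Cycle 4 assessment. Read literally, SAP 2.5.2.1 scores as an event a subject observed free of diarrhoea for all 9 weeks who withdraws at that visit.

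**What to change.** Keep the protocol-specified imputation as the primary analysis. In SAP 2.5.2.1 and 2.5.3:

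1. **Add an ITT analysis of recorded events.** Use time from first lapatinib and capecitabine dose to first Grade 2+ diarrhoea. Report day-63 cumulative incidence by arm and the difference with a 95% CI. Censor non-diarrhoea withdrawals at the withdrawal date. Give a rule for randomised subjects who never start these drugs, since they have no start date for this clock.
2. **State how progression and death are handled.** Treating them as competing events estimates incidence in their presence and does not remove all attenuation. With constant hazards and 19.6% progression or death by week 9, 20% v 6% becomes 18.0% v 5.4%, or 12.6 points.
3. **Tabulate by arm** the recorded 9-week events, the imputed events, and the withdrawal reason behind each imputed event. Link to the AE record as well as the reason field, because Protocol 4.3.2 codes voluntary stopping for toxicity simply as an AE.
4. **Reconcile** Protocol 4.3.2 with 4.3.3 on whether early progression or death is withdrawal or completion, and use one cut-off throughout.

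The cost is SAP wording before database lock, one table and one cumulative-incidence run on AE dates, withdrawal dates and reasons already in the eCRF. The downside is that the added analysis assumes uninformative censoring, which is a further reason to keep the imputed result beside it.

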2.5.2.2 Diarrhoea of Grade 2 and above during the entire treatment period

The proportion of subjects experiencing at least one episode of diarrhoea with a severity of Grade 2 or higher during the entire treatment period will be summarised using the same methods as described for [Section 2.5.2.1](#). There will not be any statistical test performed for this endpoint.

Episodes of diarrhoea ‘during the entire treatment period’ are defined as those with an onset date on or after the efficacy reference start date as defined in [Section 2.1.3.2](#) and on or before the End of Study/Withdrawal visit date.

2.5.3 Handling of missing values/censoring/discontinuations

Diarrhoea with a severity of 2 or higher during the first 9 weeks (i.e., 3 cycles treatment): Subjects who withdraw from the study on or prior to the Cycle 4 visit date will be assumed to have experienced diarrhoea (non-responder imputation) of grade 2 or higher. Such an imputation techniques will be used for the ITT and m-ITT population analysis of the primary endpoint. No imputation will be performed for the Per Protocol analyses.

Diarrhoea with a severity of 2 or higher during the entire treatment period: Subjects who do not have diarrhea event prior to the End of Study/Withdrawal visit date will be considered as non-responders and no imputation will be done in such cases.

2.5.4 Supportive analyse

Supportive analyses of the primary endpoint will be conducted using the m-ITT and PP populations, using the same methods as defined for the primary analysis. The primary endpoint will be summarized using the m-ITT and PP populations, but there will not be any statistical test performed for these populations.

No imputation will be used for the PP analysis, i.e., patients without any diarrhea event on or before desired timepoint will not be imputed and considered as non-responders.

2.5.5 Subgroup analyses for the primary endpoint

Not Applicable.

2.6 Analysis of the secondary objective

2.6.1 Investigator-reported endpoints

These analyses will be based on data reported by the investigator in the eCRF. Analyses of secondary diarrhoea-related endpoints and disease efficacy will be conducted for the ITT population.

2.6.1.1 Diarrhoea of Grade 3 and above

The proportion of subjects experiencing at least one episode of diarrhoea with a severity of Grade 3 or higher during the entire treatment period will be summarised using the same methods as described for [Section 2.5.2](#), diarrhoea of Grade 2 and above.

2.6.1.2 Diarrhoea of any grade

The proportion of subjects experiencing at least one episode of diarrhoea of any grade of severity during the entire treatment period will be summarised using the same methods as described for [Section 2.5.2](#) diarrhoea of Grade 2 and above.

A by-subject listing of all diarrhoea events will be presented in the form of an adverse event listing, including the duration and time to onset of each event.

